6.1.1. Medical Devices

The GSK manufactured medical devices (or devices manufactured for GSK by a third party) provided for use in this study are injection devices:

- A pre-filled syringe contained within a safety syringe device. The devices used in the study are representative of the devices planned to be marketed for the product.
- The components that comprise the pre-filled syringe (glass barrel with pre-staked needle and plunger) are sourced from Becton Dickinson. The pre-filled syringe is filled and assembled at GSK, Barnard Castle.
- The safety syringe components are manufactured by Becton Dickinson. The safety syringe components are assembled with the pre-filled syringe at GSK, Barnard Castle.

The Instruction for use (IFU) of the injection device will be provided. The instructions were developed and optimised as a result of formative human factors studies for mepolizumab and are representative of those that are planned for GSK3511294.

All device deficiencies (including malfunction, use error and inadequate labelling) shall be documented, and reported by the investigator throughout the clinical investigation (see Section 8.3.8) and appropriately managed by GSK.

6.2. Preparation/Handling/Storage/Accountability

- The investigator or designee must confirm appropriate temperature conditions have been maintained during transit for all study intervention received and any discrepancies are reported and resolved before use of the study intervention.
- Only participants enrolled in the study may receive study intervention and only authorised site staff may supply or administer study intervention.
- All study interventions must be stored in a secure, environmentally controlled, and monitored (manual or automated) area in accordance with the labelled storage conditions with access limited to the investigator and authorised site staff.
- The investigator, institution, or the head of the medical institution (where applicable) is responsible for study intervention accountability, reconciliation, and record maintenance (i.e., receipt, reconciliation, and final disposition records).
- Further guidance and information for the final disposition of unused study intervention are provided in the Study Reference Manual.
- Under normal conditions of handling and administration, study intervention is not expected to pose significant safety risks to site staff. Take adequate precautions to avoid direct eye or skin contact and the generation of aerosols or mists. In the case of unintentional occupational exposure, notify the monitor, Medical Monitor and/or GSK study contact.

- A Material Safety Data Sheet (MSDS)/equivalent document describing occupational hazards and recommended handling precautions either will be provided to the investigator, where this is required by local laws, or is available upon request from GSK.

6.3. Measures to Minimize Bias: Randomization and Blinding

This is an open-label study, randomization is not applicable. In order to maintain the blind from previous studies, WBC differential (% and total) will be blinded at screening [REDACTED]. Sites to continue the blinding strategy from 206713 and 213744 studies [REDACTED]

6.4. Study Intervention Compliance

GSK3511294 will be administered under medical supervision via SC injection to participants by the investigator or designee at the study site. Dose administration details (date and time) will be recorded in the source documents and reported in the CRF.

Participants will be monitored in clinic for a minimum of 2 hours post-dose to monitor for immediate hypersensitivity and any other untoward event (For details refer to SRM). In the event of an acute severe reaction (e.g., anaphylaxis) following administration of GSK3511294, there are personnel/staff onsite at the treatment facility who are appropriately trained in basic life support to manage the participant including administration of medications (e.g., epinephrine), and have access to a system that can promptly transport the participant to another facility for additional care if appropriate.

6.5. Dose Modification

Dose modification is not allowed.

6.6. Continued Access to Study Intervention after the End of the Study

Participants will not receive any additional treatment from GSK after completion of the study. The investigator is responsible for ensuring that consideration has been given to the post-study care of the participant's medical condition.

6.7. Treatment of Overdose

The dose of GSK3511294 that is considered to be an overdose has not been defined. There are no known antidotes and there is no specific treatment for a suspected overdose. In FTIH study 205722 [GSK Document Number [RPS-CLIN-044550](#) or later], single SC doses of GSK3511294 up to 300 mg were well tolerated by adult participants with mild/moderate asthma (6 participants received a 300 mg SC dose).

Each PFS will enable the delivery of a single dose of study intervention (see Section [6.1](#)).

In the event of an overdose, the investigator should:

- Contact the Medical Monitor immediately.
- Treat the patient with active supportive care as dictated by the participant's clinical status in the knowledge of the long half-life (approximately 41 days) of GSK3511294.
- Closely monitor the participant for AE/SAE and laboratory abnormalities for 30 weeks following the last administered dose.
- Document the quantity of the excess dose as well as the duration of the overdosing in the CRF.

Decisions regarding discontinuation or delay of another dose of study intervention will be made by the investigator in consultation with the Medical Monitor based on the clinical evaluation of the participant.

6.8. Concomitant Therapy

At enrolment, information on the participant's baseline SoC asthma therapy will be collected and recorded in the eCRF.

Any medication or vaccine (including over the counter or prescription medicines, recreational drugs, vitamins, and/or herbal supplements) that the participant is receiving at the time of enrolment or receives during the study must be recorded along with:

- reason for use
- dates of administration including start and end dates
- dosage information including dose and frequency

The Medical Monitor should be contacted if there are any questions regarding concomitant or prior therapy.

6.8.1. Permitted Medications and Non-Drug Therapies

Throughout the study, participants are to be maintained on SoC asthma treatment. During the study, adjustments may be made to participant's asthma maintenance therapy based on the investigator's judgment.

If uncertain whether a medication is permitted, please confirm with the Medical Monitor.

Albuterol/salbutamol is permitted throughout the study but should, if possible, be withheld in the 6-hour period prior to spirometry assessments.

LABAs, LAMAs, ICS/LABA or ICS/LABA/LAMA fixed dose combinations should be withheld for ≥ 12 hours prior to spirometry, if possible.

Continuous Positive Airway Pressure (CPAP) or Bilevel Positive Airway Pressure (BiPAP) for the treatment of obstructive sleep apnoea is permitted. This treatment must be captured in the eCRF.

Participants can be vaccinated against SARS-CoV-2 infection using authorized COVID-19 vaccines in line with local/national guidelines for COVID-19 vaccines. Experimental COVID-19 vaccines are not permitted.

COVID-19 vaccination is permitted and should follow local regulations. COVID-19 vaccine administration and the study site injection should be separated by 14 days if possible, in order to be able to properly assess study injection site/treatment reactions.

6.8.2. Prohibited Medications and Non-Drug Therapies

The following medications are not allowed during the study:

Medication

Monoclonal antibodies and Investigational drugs

- Any investigational drug/vaccine.
- Mepolizumab [Nucala], reslizumab [Cinquiry/Cinquaero], benralizumab [Fasenra], Omalizumab [Xolair], dupilumab [Dupixent]
- Other monoclonal antibodies
- Experimental anti-inflammatory drugs (non-biologicals)

Immunosuppressive medications such as those listed below (not all inclusive)

- Regular systemic (oral or parenteral) and intramuscular, long-acting depot corticosteroids if used to treat a condition other than asthma
- Methotrexate, cyclosporin, azathioprine
- Oral gold
- Chemotherapy used for conditions other than asthma

Additionally, Bronchial Thermoplasty and Radiotherapy are excluded throughout the study.

6.8.3. Rescue Medicine

Trade label albuterol/salbutamol metered dose inhalers (MDIs) will be provided as rescue medication throughout the study. Albuterol/salbutamol will be sourced for all centres. Low dose ICS-formoterol as rescue medication is not allowed.

Participants will be dispensed an MDI at Visit 1 to be used primarily to treat asthma symptoms on an as needed basis (see Section 8.4.3). The MDI should be replaced as needed.

Although the use of rescue medications is allowable (at any time during the study), the use of rescue medications should be delayed, if possible, for at least 6 hours prior to the spirometry assessments.

7. DISCONTINUATION OF STUDY INTERVENTION AND PARTICIPANT DISCONTINUATION/WITHDRAWAL

7.1. Discontinuation of Study Intervention

No further doses of study intervention will be administered to participants who meet any of the following permanent treatment discontinuation conditions at any time during the study treatment period:

- Meets any of the protocol-defined liver chemistry stopping criteria, (see Section 7.1.1)
- ECG: meets any of the protocol-defined QTc stopping criteria (see Section 7.1.3)
- Pregnancy: Positive pregnancy test (see Section 8.2.5)
- Severe allergic reaction/anaphylaxis: Participants with severe allergic reaction/anaphylaxis with no clear alternative cause (see Appendix 8)
- Vasculitis: Participants with confirmed vasculitis or suspected vasculitis with no alternative explanation (see Section 7.4).

If a participant meets any of the treatment discontinuation conditions or chooses (for any reason) not to receive an additional dose of study intervention before the end of the protocol specified intervention period:

- The Investigator will make every effort to encourage the participant to remain in the study and to continue with all remaining study visits, including the Exit Visit and Follow-up Visit/call.
- The primary reason for discontinuation of study intervention (e.g., AE, lack of efficacy, protocol deviation, investigator discretion, consent withdrawn etc.) must be recorded in the eCRF.
- Participants will be provided with the option to continue to have regularly scheduled in-clinic visits or to have regularly scheduled phone visits. The required study assessments will depend on whether the participant is attending an in-clinic visit or a scheduled phone visit. At a minimum, an assessment of exacerbations, AEs, SAEs, and concomitant medications will be completed.
- If for any reason, the participant later chooses to withdraw from the study, a Withdraw from Study Visit (see Section 7.2) should be conducted according to the SoA (Section 1.3).

[figure not shown]
7.1.1. Liver Chemistry Stopping Criteria

Liver chemistry stopping criteria, and increased monitoring criteria have been designed to assure participant safety and evaluate liver event aetiology.

Discontinuation of study intervention for abnormal liver tests is required when:

- a participant meets one of the conditions outlined in the algorithm or
- in the presence of abnormal liver chemistry not meeting protocol-specified stopping rules, if the investigator believes that it is in the best interest of the participant.

[figure not shown]
Liver Chemistry Stopping Criteria Algorithm

Abbreviations: ALT = alanine transaminase; INR = international normalised ratio; SAE = serious adverse event; ULN = upper limit of normal, Tbili = Total bilirubin

Refer to [Appendix 6](#), for required Liver Safety Actions, Monitoring and Follow up Assessments.

Liver Chemistry Increased Monitoring Algorithm with Continued Study
Intervention for Participants with ALT ≥ 3 xULN but < 8 xULN and do not meet any of the liver stopping criteria

Abbreviations: ALT = alanine transaminase; Tbili = total bilirubin; INR = international normalised ratio; SAE = serious adverse event; ULN = upper limit of normal, Tbili = Total bilirubin.

Refer to [Appendix 6](#), for required Liver Safety Actions, Monitoring and Follow up Assessments.

7.1.2. Rechallenge

7.1.2.1. Study Intervention Restart or Rechallenge after liver stopping criteria met

Study intervention restart or rechallenge after liver chemistry stopping criteria are met by any participant in this study is not allowed.

7.1.3. QTc Stopping Criteria

Details on performing ECG assessments can be found in Section [8.2.3](#).

The QT interval corrected using Fridericia's formula (QTcF) must be used for each individual participant to determine eligibility for and discontinuation from the study intervention. This formula may not be changed or substituted once the participant has been enrolled. For this study, the following QTc stopping criteria will apply:

- QTcF >500 msec OR Uncorrected QT >600 msec
- Change from Baseline of QTcF >60 msec

For participants with underlying bundle branch block, follow the discontinuation criteria listed below:

| Baseline QTcF with Bundle Branch Block | Discontinuation QTcF with Bundle Branch Block |
|--|---|
| <450 msec | >500 msec |
| 450 – 480 msec | ≥530 msec |

The QTcF value from the 12-lead ECG central over-read at Visit 1 should be used as baseline QTcF value for any changes from baseline calculations during the study. Twelve-lead ECG central overread values should be used at all visits with the exception of Visit 1 and Visit 6 where 12-lead ECG machine read values should be used. After Visit 1 12-lead ECG central over-read values should be used to assess QTc stopping criteria, with the exception of Visit 6 (Week 26) where 12-lead ECG machine read values should be used.

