| Study Day | 1 | 28 | 56 | 84 | 140 | 182 | 196 | 224 | 252 | 280 | 336 | 364 | 392 | | | |
| Vital Signs | X ^d | | X | | X | X | X | | | X | | X ^d | | X ^d | | See footnote d. |
| 12-lead ECG | (X) | X | | | | X | X | | | | | | X | | X | ECG must be performed and assessed pre-dose. Twelve-lead ECG central overread values should be used at all visits with the exception of Visit 1 and Visit 6 where 12-lead ECG machine read values should be used. |
| Adverse Events/Serious Adverse Event Assessment | X ^e | X | X | X | X | X | X | X | X ^h | X | X ^h | X | X | X | | See footnote e. |
| Laboratory Assessments | | | | | | | | | | | | | | | | See footnote f. All WOCBP as determined in prior study (206713/ 213744) must continue their highly effective contraceptive method without any interruptions between prior study and enrolment in this study. See Section 5.1 and Section 8.2.5 for additional details |
| Urine Pregnancy Test ^f (WOCBP only) | X | X | X | X | X | X | X | X | X ^h | X | X ^h | X | X | X | | |

CONFIDENTIAL

212895

Protocol Amendment 2

| Protocol Activity | | Intervention Period and Exit Visit (visit window is ± 7 days) | | | | | | | | | | | | Follow-up visit/call or Withdrawal Visit (± 7 days) | Notes | |
|-------------------------|------|---|----|----|-----|-----|-----|-----|----------------|-----|----------------|-----|----------------|--|-----------------------|--|
| | | V1 * | V2 | V3 | V4 | V5 | V6 | V7 | V8 | V9 | V10 | V11 | Exit Visit V12 | FU ^a | WS Visit ^b | |
| Visit | V1 * | | | | | | | | | | | | | | | FU=Follow-up visit WS=Withdrawn from study visit |
| Study Week | 0 | 4 | 8 | 12 | 20 | 26 | 28 | 32 | 36 | 40 | 48 | 52 | 56 | | | |
| Study Day | 1 | 28 | 56 | 84 | 140 | 182 | 196 | 224 | 252 | 280 | 336 | 364 | 392 | | | |
| Urinalysis | (X) | | | | | | X | | | | | | | X | | Note: Urinalysis to be performed using dipstick test. If results are abnormal a second urine sample should be taken and sent to central laboratory. China Only: For China sites the urine specimen may be sent to the central laboratory for routine urinalysis instead of performing a local urine dipstick. |
| Clinical Chemistry | (X) | X | X | X | X | X | X | | | X | | X | | X | | Include liver chemistry. |
| Immunogenicity sample | (X) | | | X | | X | | | | X | | X | | X | | |
| CC1 | | | | | | | | | | | | | | | | CC1 |
| Efficacy Assessments | | | | | | | | | | | | | | | | |

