| Protocol Activity | | Intervention Period and Exit Visit (visit window is ± 7 days) | | | | | | | | | | | Follow-up visit/call or Withdrawal Visit (± 7 days) | Notes | |
|-------------------|------|---|----|----|-----|-----|-----|-----|-----|-----|-----|----------------|--|-----------------|-----------------------|
| | | V2 * | V3 | V4 | V5 | V6 | V7 | V8 | V9 | V10 | V11 | Exit Visit V12 | | | |
| Visit | V1 * | 0 | 4 | 8 | 12 | 20 | 26 | 28 | 32 | 36 | 40 | 48 | 52 | FU ^a | WS Visit ^b |
| Study Week | | 28 | 56 | 84 | 140 | 182 | 196 | 224 | 252 | 280 | 336 | 364 | 392 | | |
| Study Day | | 1 | | | | | | | | | | | | | |
| CC1 | | | | | | | | | | | | | | | |

*: If the Exit Visit in 206713/213744 is on the same day, or within 7 days of Visit 1 for study 212895 then the assessments in brackets above do not need to be performed and the assessments from the Exit Visit from 206713/213744 will be used as the baseline for 212895. Information will be transferred accordingly. If the Visit 1 performed greater >7 days (maximum 14 days) after the Exit Visit in 206713/213744 then the assessments in brackets needs to be performed (For details refer to Section 8). A delayed administration of the study intervention (maximum 4 weeks) may be considered in consultation with the GSK Medical Monitor.

- a. Informed Consent must be obtained prior to initiating any study assessments.
- b. If a participant withdraws from the study, then the Withdraw from Study (WS) Visit should be conducted 26 weeks after the last administered dose of study intervention, i.e., at Week 26 if the participant withdraws before the second dose of study intervention, or at Week 52 if the second dose of study intervention was received.
- c. Ensure maintenance asthma medications from the previous trial to Visit 1 and all current medications are reviewed.
- d. Vital signs including height and weight should be conducted at Visit 1. Height can be omitted for subsequent visits.
- e. SAEs must be collected after signing of Informed Consent.
- f. Urine pregnancy testing is only required for women of childbearing potential (WOCBP). Serum pregnancy test is required at the Exit Visit of the parent protocols for all WOCBP.

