5.2. Exclusion Criteria

Participants are excluded from the study if any of the following criteria apply:

MEDICAL CONDITIONS

1. **Health Status:** Clinically significant change in health status during Study 206713 or Study 213744 which in the opinion of the investigator would make the participant unsuitable for participation in this study.

MEDICAL CONDITIONS

2. **Malignancy:** A current malignancy or a malignancy that developed during Study 206713 or Study 213744 (participants who had localised carcinoma of the skin that was resected for cure will not be excluded).
3. Participants who have other clinically significant medical conditions uncontrolled with SoC therapy not associated with Asthma, e.g., uncontrolled cardiovascular disease or ongoing active infectious disease which in the opinion of the investigator makes them unsuitable for the study.
4. Participants with known parasitic (helminth) infections within 6 months prior to Visit 1 will be excluded from the study or required to be adequately treated for helminth infections before initiation of GSK3511294.
5. Liver chemistry test: Participants who meet the following based results of week 48 assessment from Study 206713 or Study 213744 or from a later result:
 - a) Alanine aminotransferase (ALT) $>2\times$ upper limit of normal (ULN)
 - b) Total bilirubin $>1.5\times$ ULN (isolated bilirubin $>1.5\times$ ULN is acceptable if bilirubin is fractionated and direct bilirubin $<35\%$)
 - c) Liver Disease: Cirrhosis or current unstable liver or biliary disease per investigator assessment defined by the presence of ascites, encephalopathy, coagulopathy, hypoalbuminaemia, oesophageal or gastric varices, persistent jaundice.

NOTE: Stable non-cirrhotic chronic liver disease (including Gilbert's syndrome, asymptomatic gallstones, and chronic stable hepatitis B or C) are acceptable if participant otherwise meets eligibility criteria.
6. Vasculitis: Participants with current diagnosis of vasculitis. Participants with high clinical suspicion of vasculitis at screening will be evaluated and current vasculitis must be excluded prior to enrolment.
7. ECG Assessment: QTcF ≥ 450 msec or QTcF ≥ 480 msec for participants with Bundle Branch Block in the 12-lead ECG machine read at Visit 1.

OTHER EXCLUSIONS

8. Smoking status: Current smokers
9. Hypersensitivity: Participants with allergy/intolerance to the excipients of GSK3511294 in Section 6.1, a monoclonal antibody, or biologic.

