8.2.3. Electrocardiograms

- Twelve-lead ECGs will be obtained at the time points specified in the SoA (see Section 1.3) using an ECG machine, provided by GSK via a designated central laboratory, that automatically calculates the heart rate and measures PR, QRS, QT, and QTc intervals.
- The QTcF formula must be used for *each* individual participant to determine eligibility. This formula may not be changed or substituted once the participant has been enrolled. Refer to Section 7.1.3 for the QTcF formula.
- If an ECG demonstrates a prolonged QT interval, obtain two more ECGs over a brief period, and then use the averaged QTcF values of the three ECGs to determine whether the patient should be enrolled or discontinued from the study intervention (but not from the study). Refer to Section 5.2 for exclusion criteria related to ECG assessment and Section 7.1.3 for QTc withdrawal criteria and additional QTc readings that may be necessary.
- ECG measurements will be made after the subject has rested in the supine position for 5 minutes. The ECG should be obtained after the vital signs assessments but before lung function testing followed by other study procedures. Collection shortly after a meal or during sleep should be avoided since QT prolongation can occur at these times.
- Paper ECG traces will be recorded at a standard paper speed of 25 mm/sec and gain of 10 mm/mV, with a lead II rhythm strip. There will be electronic capture and storage of the data by a validated method.

- Paper ECG traces are required to be maintained at the site with other source documents.

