| Section 1.3 and Schedule of Activities (SoA), Section 10.9 Appendix 9: Recommended Measures Related to COVID-19 Pandemic (Table 4) | Moved note (see footnote d) from Physical examination to Vital signs. | Clarification |
| Section 1.3 and Schedule of Activities (SoA), Section 10.9 Appendix 9: Recommended Measures Related to COVID-19 Pandemic (Table 4) | Administer Study intervention: Modified the text in notes as follows: Study intervention will only be administered in the clinic. Any scheduled assessments or sample draws should be performed beforehand. Monitor participant for hypersensitivity for at least 2 h after IP administration. For details refer to study reference manual (SRM). | Clarification |
| Section 1.3 and Schedule of Activities (SoA), Section 10.9 Appendix 9: Recommended Measures Related to COVID-19 Pandemic (Table 4) | Add notes to SoA referencing for ECG and new wording as below, ECG must be performed and assessed pre-dose. Twelve-lead ECG central overread values should be used at all visits with the exception of Visit 1 and Visit 6 where 12-lead ECG machine read values should be used. | Clarification on ECG to be performed at pre-dose and to give clarification on usage of twelve-lead ECG central overread and machine read values for QTcF exclusion and discontinuation criteria. |
| Section 1.1 and Synopsis, Section 1.3 and Schedule of Activities (SoA), Section 4.1 Overall design, Section 10.9 Appendix 9: Recommended Measures Related to COVID-19 Pandemic (Table 4) | Added new footnote "i" with new wording as below: For WOCBP the follow up visit should be conducted as onsite visit or home visit (where applicable). Follow-up phone call is only applicable for male and WONCBP. | Clarification |
| Section 1.3 and Schedule of Activities (SoA), Section 10.9 Appendix 9: Recommended Measures Related to COVID-19 Pandemic (Table 4) | Updated footnote "h" with new wording as below: In France, Week 36 and Week 48 are phone visits for all participants except WOCBP who will need to perform both visits, including the Follow Up visit, onsite. | France EC recommendations |
| Section 1.3 and Schedule of Activities (SoA), Section 10.9 Appendix 9: Recommended Measures Related to COVID-19 Pandemic (Table 4) | Removed follow up visit/call conducted 30 weeks after the last dose of study intervention for AE/SAE assessments and pregnancy testing from footnote "b" and added as a new footnote "i". | Clarification |

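### The Week 26 QTcF change test that decides the second dose sets a machine read against a central over-read baseline, and the published SAP names no read source

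*Protocol*

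**What the plan says.** Protocol 7.1.3 lists among its stopping criteria "Change from Baseline of QTcF >60 msec". For the baseline it says "The QTcF value from the 12-lead ECG central over-read at Visit 1 should be used as baseline QTcF value", and it applies this to every change calculation in the study. After Visit 1 it assesses the stopping criteria on central over-reads, "with the exception of Visit 6 (Week 26) where 12-lead ECG machine read values should be used". Visit 6 is the visit at which the second dose is given (Protocol 6).

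Eligibility is decided on the other method: exclusion 7 in Protocol 5.2 takes QTcF "in the 12-lead ECG machine read at Visit 1". The ECG note in the Schedule of Activities (Protocol 1.3) says in general terms "Twelve-lead ECG central overread values should be used at all visits with the exception of Visit 1 and Visit 6", where the machine read applies. The Amendment 1 entry in Protocol 10.11 gives the purpose of that note as clarifying "usage of twelve-lead ECG central overread and machine read values for QTcF exclusion and discontinuation criteria".

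The SAP's version history bases all three versions on the protocol of 30 July 2021. Amendment 1, which added the read-source rule, is dated 12 January 2023. SAP 4.1.2 (baseline), 4.5.3.3 (QTcF change, maximum and maximum increase) and 6.2.5 (repeated ECGs) do not say whether machine reads or over-reads are used.

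**The concern.** A change score is like for like only if both values come from the same method. At Week 26 they do not. Suppose the machine reads b msec higher than the over-read on average. A participant whose like-for-like change lies between 60 - b and 60 msec would then meet the criterion and lose the second dose (Protocol 2.3.1 and 7.1). If the machine reads b msec lower, a participant whose change lies between 60 and 60 + b would be dosed when the rule meant to stop them. QTc prolongation is an adverse event of special interest (Protocol 8.3.7), and this visit is the one where the test decides dosing on the day.

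The need to assess the ECG before dosing explains the machine read at Week 26. It does not explain the over-read baseline.

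**Working it through.** The documents give no figure for this rule, so there is none to reproduce. The first step is textual and the second is an illustration.

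**Step 1: which read goes into each comparison (Protocol 7.1.3 and 1.3)**

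| ECG visit | Post-baseline value | Baseline value | Comparison |
|---|---|---|---|
| Week 4 | over-read | over-read | like for like |
| Week 26 (dose 2) | machine | over-read | mixed |
| Week 28 | over-read | over-read | like for like |
| Week 52 | over-read | over-read | like for like |

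Only the change criterion at Week 26 is mixed. The absolute limits (QTcF above 500 msec, uncorrected QT above 600 msec) subtract no baseline.

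**Step 2: how many participants this could touch**

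Inputs:
- Threshold: 60 msec (Protocol 7.1.3).
- n = 637, the planned enrolment (Protocol 9.2; 750 × 0.85 = 637.5). Fewer may reach Week 26.
- Assumed: SD s of the change, 15 or 20 msec; machine-minus-over-read offset b, from -10 to +10 msec; normal changes with mean zero apart from b.

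Formula for a single read: expected count = 637 × [1 - Φ((60 - b)/s)].

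| b (msec) | s = 15 | s = 20 |
|---|---|---|
| -10 | 0.001 | 0.15 |
| -5 | 0.005 | 0.37 |
| 0 | 0.02 | 0.86 |
| +5 | 0.08 | 1.90 |
| +10 | 0.27 | 3.96 |

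Example: s = 20, b = +10 gives (60 - 10)/20 = 2.5, a tail of 0.00621, and 637 × 0.00621 = 3.96. Against 0.86 with no offset, about 3.1 of these come from the offset. At b = -10 the count falls by about 0.7.

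**Step 3: the repeat-ECG rule**

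Protocol 8.2.3 asks for two more ECGs when QT is prolonged and decides on the mean of three. Assume that a rise above 60 msec triggers this, and that a share w of the variance is within-visit. The mean of three then has SD s × √(1 - w + w/3), and its correlation with the first read is √(1 - w + w/3). The count becomes 637 × P(first read > 60 and mean > 60).

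For s = 20:
- w = 0.25: SD of the mean 18.3, correlation 0.91. Count 1.4 at b = +10, against 0.22 at b = 0.
- w = 0.50: SD of the mean 16.3, correlation 0.82. Count about 0.4 at b = +10, against 0.05 at b = 0.

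For s = 15 and b = +10, the count falls from 0.27 to 0.06 (w = 0.25) or 0.01 (w = 0.50). Averaging shrinks the random part and leaves b untouched.

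**Step 4: sensitivity**

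Mixing methods may also add scatter. With a further 10 msec between-method SD, s = 20 becomes √(400 + 100) = 22.4. The single-read count is then 2.3 at b = 0 and 8.1 at b = +10, before any averaging. This input is also an assumption.

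**The case against.** **The machine read at Visit 6 is needed for a same-day decision.** This stands. But a machine baseline should also exist: exclusion 7 relies on one, and the machine is of a type "that automatically calculates the heart rate and measures PR, QRS, QT, and QTc intervals".

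**The effect on dosing is close to nil and rests on chosen inputs.** Largely this stands. Offset, SD and scatter are all absent from the documents. Within ±5 msec, and with no added scatter, the expected count stays below 2 of 637. The three-ECG mean lowers it further, although Protocol 8.2.3 speaks of a prolonged QT interval and does not say that a change above 60 msec triggers repeats.

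**A machine baseline would give each participant two baseline values, and it may not be held for everyone.** This stands as a cost. When Visit 1 falls within 7 days of the parent study's exit visit, "the assessments from the Exit Visit from 206713/213744 will be used as the baseline for 212895".

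**A reader might infer that the QTcF tables mix methods too.** The documents do not support that. The Amendment 1 rationale ties the read-source note to exclusion and discontinuation. In Protocol 7.1.3 the rule sits under stopping criteria, and its last sentence restates it for those criteria. Taken literally for reporting, the visit rule would also make Visit 1 a machine read, against the over-read baseline set in the same paragraph. The SAP defers output detail to an Output and Programming Specification that is not available here, and redacted text follows SAP 4.5.3.3, so the source may be named there. What remains is that the SoA wording is not limited to dosing decisions and the visible SAP does not settle the matter.

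**Conclusion.** The mixed comparison is the written rule for the Week 26 change test, and nothing elsewhere in the protocol corrects it. Confidence in that is high. Its practical size is small and cannot be established from the documents. With SDs of 15 to 20 msec, offsets up to 10 msec and no added scatter, the expected number above the limit is from near zero to about 4 of 637 on one read. At the upper end it is about 0.4 to 1.4 once the three-ECG mean applies.

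It would be wrong to conclude that participants are being wrongly stopped or wrongly dosed, because no offset is documented. No bias in the reported tables is shown either; that would need the literal visit wording to be carried into reporting. ECG change is in any case listed under Other endpoints, and a shift confined to Week 26 could be seen against Week 28. This is an inexpensive improvement to a dosing rule and a clarification of the SAP.

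**What to change.** 1. **Protocol 7.1.3.** State that the same-day Week 26 test of a rise above 60 msec compares the Week 26 machine read with the baseline machine read used for exclusion 7. Keep the present comparison only where that read is not held. Leave the absolute limits on the machine read as they are.
2. **SAP 4.1.2 and 4.5.3.3.** State that all QTcF summaries (baseline, change, maximum, maximum increase) use the central over-read at every visit, including Week 26 and a baseline copied from the parent exit visit. Machine reads serve only same-day eligibility and dosing decisions.

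The cost is a short protocol clarification and one SAP sentence. The downside is a second baseline value per participant, used for this one test, and a different comparison for anyone without a machine baseline. The sponsor must first confirm that Visit 6 over-reads and baseline machine reads are held, including for baselines carried over from the parent studies. If they are, no new data collection is needed.
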